6.3. Operational Definitions

- Fever : temperature recorded $\geq 37.5^{\circ}\text{C}$ during the first 24 hours period of hospitalization or at home.
- Study specimens: specimens collected from study subjects.

- Respiratory samples: leftover respiratory samples (BAL, pleural fluid, etc) that are collected by the attending physician based on clinical presentation.
- Study clinical data: clinical data collected from study subjects.
- Study completion: Subjects followed until 30- days (\pm 4-days window period) after hospitalization or die.
- Subject withdrawal: if the subject's parents or legal guardians decides to voluntarily discontinue participation or the study physician decides to terminate subject participation at any time during the study.
- Missed visit: a scheduled study visit which a study subject fails to attend or a home visit does not occur.

7. REPORTING THE LOSS OR UNANTICIPATED DESTRUCTION OF SPECIMENS/ DATA TO THE IRB

Any loss or unanticipated destruction of data or samples (for example, due to freezer malfunction) that compromises the scientific integrity of the data collected for the study will be reported to the IRB. Additionally, participants may decide at any point not to have their samples stored. In this case, the principal investigator will destroy all known remaining samples and report what was done to both the participant and to the IRB.

8. RESEARCH MONITORING

The study will be conducted in compliance with this protocol, the International Conference on Harmonization (ICH) Guideline for Good Clinical Practice (GCP), and any applicable regulatory and ethical requirement(s). Independent monitors, under contract by the Sponsor, will visit the study sites to monitor all aspects of the study in accordance with the monitoring plan. The objective of a monitoring visit is to oversee the progress of the study, and of ensuring that it is conducted, recorded, and reported in accordance with the protocol, Standard Operating Procedures (SOPs), Good Clinical Practice (GCP), and the applicable regulatory requirement(s).

Site investigators will allow study monitors to inspect study facilities and documentation (e.g., ICF, clinic and laboratory records, other source documents, CRFs), as well as observe the performance of study procedures. Investigators also will allow inspection of all study-related

documentation by authorized representatives of the local IRB or ethic committee (EC), the local and national regulatory authorities, and the sponsor representatives. A site visit log will be maintained at the study site to document all study monitoring and auditing visits.

9. SAFETY MONITORING AND REPORTING

All reportable adverse events (events that occur within 48 hours of the study specimen collection and are possibly, probably, or definitely related to the study specimen collection) that result in a serious outcome (Serious Adverse Event (SAE)) will be evaluated by Site PI within 24 hours of the investigator's awareness. The SAE will also be reported to the IRB within 10 working days, **or follows on local ethic requirement**, of the investigator's awareness.

All reportable adverse events (events that occur within 48 hours of the research blood draw and are possibly, probably, or definitely related to the research blood draw) will be reported in the summary form to the IRB at the time of Continuing Review.

All reportable event (RE) and unanticipated problem (UP) will be reported by the site PI to the IRB within 10 working days, or follows on local ethic requirement, of the investigator's awareness as required for US federally funded trials.

9.1. Definition of an Adverse Event

An adverse event (AE) is any untoward or unfavorable medical occurrence in a human subject that occurs within 48 hours of a study-related study blood specimen collection that is possibly, probably, or definitely related to the study specimen collection. Any event outside of this 48 hours' window period will not be considered an AE for this study.

But for induce sputum collection, if the subject's conditions worsening from the original condition prior to the enrollment is observed such as, but not limited to, increase in coughing or wheezing, it will be considered as AE for this study if occurred within 2 hours after sputum induction procedure. For every AE that occurs based on the subject's conditions, the RA needs to consult with the site PI or site Co-PI to determine AE or not.

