4.6.2. Baseline (study visit day 0 = day 1 hospitalization)

Following baseline procedures will be collected on all participants, these include:

1. Demographic data including age, sex, birth order, parent's education, parent's occupation, and family income.
2. Medical history including history of mother's pregnancy and breastfeeding, vaccination, vitamin A supplementation, growth and development, history of past and presence illness including congenital disease, and allergic.
3. Clinical data including chief complaint, sign and symptoms, vital signs, anthropometric, initial diagnosed, comorbidities, chest X-Ray (if available).
4. Treatment including antibiotic, steroid, and oxygen therapy.
5. Risk factors including smoking exposure, TB contact, poultry contact (contact with sick and/or dead poultry and contact with poultry's faeces

and/or derivative), contact with someone who has cold, air pollution exposure, going to daycare, living in a densely populated area.

6. Laboratory examinations including CBC test, CRP, PCT, Blood gas analysis, blood culture, respiratory culture (if available), antimicrobial sensitivity test, HIV test, influenza rapid test, legionella Ag, Gram negative test, AFB, Xpert MTB/RIF (according to SoC).
7. Laboratory examinations at the reference laboratory including molecular and serological tests.
8. Specimen archiving including left over specimens (whole blood, serum, urine, NPS, sputum/induced sputum) and isolate from culture (if available)

Whole blood and serum must be collected and processed during 24 hours after the enrollment. Other specimens' collection can be postponed up to 48 hours after the enrollment.

Blood culture should be performed on all participants prior to antibiotic administration in the study site, however any condition where blood culture is done after the antibiotic administer is still allowed. Blood culture worked prior to the enrollment will be recorded in the CRF and no repetition needed.

For the detail of study procedures, please check out the Manual of Procedures (MoP).

4.6.3. Follow up during hospitalization (Daily study visit day 1 up to day 12 = day 2nd up to day 13th hospitalization)

This follow up schedule will be conducted daily during hospitalization of participants, but limited up to daily study visit day 12 (day 13th hospitalization). The following procedures will be collected from each participant, if available:

1. Clinical data including sign and symptoms, vital signs, and chest X-Ray.

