3.6.7. Laboratory procedures for Molecular and Serological Testing

This study will carry out molecular and serological testing that will be done at the reference laboratory. The study will cover all the costs of those tests.

Table 1 and Table 2 will furtherly explain the required specimen volume and tests needed. Also see appendix A for the work flow.

Table 1. The research specimen and laboratory testing

Visit /Time	Collected Specimen	Amount	Laboratory Testing at	
			Hospital	Reference Lab
Enrollment (up to 24 hours after enrollment)	Whole Blood	2 x 1 ml – 2 ml blood 1 x 3 ml blood	Blood culture (2 sides) CBC	PCR (Streptococcus pneumonia, Staphylococcus aureus, Haemophilus influenza)
	Serum	1 x 4 ml blood	CRP, Procalcitonin, HIV (can be done up to 5 days after enrollment)	Serology IgM and IgG (Influenza A, B, RSV, Parainfluenza virus, Adenovirus, Mycoplasma pneumonia, Chlamydia pneumonia, Bordetella pertussis, Legionella pneumonia)
Enrollment (up to 48 hours after enrollment)	Urine	1 ml – 3 ml urine	Rapid test Legionella antigen	PCR (Legionella pneumoniae, Leptospira)
	Nasopharyngeal swab	2 VTM (1.5 ml)	Rapid test Influenza Rapid test RSV	PCR (18- Viral Panel)
	Sputum/induced sputum	2 ml	Culture, MTB (genexpert, if AFB positive)	PCR (11 Bacterial and 18 viral panel)
	Other resp specimen (leftover – effusi pleura, BAL)	If available	Culture, MTB (genexpert, if AFB positive)	PCR (11 Bacterial and 18 viral panel)
Daily study visit during hospitalization	Left-over respiratory specimen and/or plasma (Daily study visit day 1 & 2 (day 2 & 3 of hospitalization)	If available	None	TBD
Study Visit Day 14th after hospitalization	Serum	4 ml blood	None	Serology IgM and IgG (Influenza A, B, RSV, Parainfluenza virus, Adenovirus, Mycoplasma pneumonia, Chlamydia pneumonia, Bordetella pertussis, Legionella pneumonia)
Follow-up Day 30 th after hospitalization	None	None	None	None

NOTE: Maximum amount of blood drawn in pediatric patients weight 7.3 – 45.5 kgs is 10 ml - 30 ml at any one time or 60 ml – 350 ml cumulative during hospitalization or maximum 1 month (Garza D, Becan-McBride K).

Table 2. PCR Panel for Bacterial & Viral Pathogens

PCR Viral Panel	PCR Bacterial Panel
Human Influenza A virus	Haemophilus influenza
Human Influenza B virus	Streptococcus pneumoniae
Adenovirus	Legionella pneumoniae
Enterovirus	Mycoplasma pneumoniae
Respiratory Syncytial Virus A	Chlamydia pneumoniae

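### The protocol gives conflicting starting points for the 48-hour AE window, so non-serious events from the swab, urine or non-induced sputum can fall outside the AE definition

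*Combined protocol and SAP*

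**What the plan says.** Section 9.1 counts an event as an AE if it "occurs within 48 hours of a study-related study blood specimen collection that is possibly, probably, or definitely related to the study specimen collection". The timing is tied to blood, whereas relatedness is to study specimen collection without that limit. An event outside the "window period will not be considered an AE for this study". Induced sputum alone has a separate rule: a worsening of the child's condition counts, and "it will be considered as AE for this study if occurred within 2 hours after sputum induction procedure". The swab, urine and sputum obtained without induction have no rule of their own.

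Section 9 uses two further wordings. Its first paragraph, on events with a serious outcome, covers "events that occur within 48 hours of the study specimen collection and are possibly, probably, or definitely related to the study specimen collection". Its second paragraph, on the summary sent to the IRB at Continuing Review, ties both timing and relatedness to the research blood draw.

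On collection times, Section 4.6.2 says "Whole blood and serum must be collected and processed during 24 hours after the enrollment", and of the remaining specimens that "collection can be postponed up to 48 hours after the enrollment". Table 1 in Section 3.6.7 places urine, nasopharyngeal swab and sputum in the row headed "Enrollment (up to 48 hours after enrollment".

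Section 9.2 defines an SAE as a kind of AE, so it inherits the 9.1 window. Section 9.3 makes a Reportable Event of anything outside the AE definition that meets a seriousness criterion.

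**The concern.** An AE definition should give the same answer for the same event at every site. Here the answer depends on which section the site reads and, under 9.1, on the order in which specimens were taken. A child swabbed together with the blood draw has the full 48 hours after the swab; a child swabbed a day and a half after the blood has 12.

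The swab is not incidental. Section 4.3 makes the influenza, RSV and Legionella rapid tests a requirement of the study, and Table 1 runs them on the swab and urine. A non-serious event related to one of these collections may not be an AE under 9.1, and it cannot be a Reportable Event because 9.3 requires seriousness. For a serious event, the question is whether it is classed as an SAE, with Site PI evaluation within 24 hours, or as a Reportable Event, for which that evaluation is not stated.

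**Working it through.** The plan gives no figure of its own to reproduce. The check is timeline arithmetic, followed by a comparison of the sections.

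**Inputs**
- b = hours from enrolment to the study blood collection, 0 to 24 (Section 4.6.2).
- s = hours from enrolment to the swab, urine or sputum collection, 0 to 48 (Section 4.6.2; Table 1).
- Window length: 48 hours from the blood collection (Section 9.1).

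**Formula.** The 9.1 window closes at b + 48, so the time left after a specimen taken at s is b + 48 − s.

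| Blood (b) | Swab (s) | Left under 9.1 | Left if timed from the swab |
|---|---|---|---|
| 0 h | 0 h | 0 + 48 − 0 = 48 h | 48 h |
| 0 h | 24 h | 0 + 48 − 24 = 24 h | 48 h |
| 0 h | 36 h | 0 + 48 − 36 = 12 h | 48 h |
| 12 h | 48 h | 12 + 48 − 48 = 12 h | 48 h |
| 24 h | 48 h | 24 + 48 − 48 = 24 h | 48 h |
| 0 h | 48 h | 0 + 48 − 48 = 0 h | 48 h |

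Whenever s exceeds b, fewer than 48 hours remain. The minimum over the permitted times is 0, reached only at b = 0 and s = 48; it is never negative.

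**Illustration only.** The documents give no distribution of collection times. If b and s were independent and uniform over their permitted ranges:
- mean time left = 12 + 48 − 24 = 36 h;
- share with under 48 h = 1 − 12/48 = 75%;
- share with under 24 h = 12/48 = 25%;
- share with under 2 h = (½ × 2 × 2)/(24 × 48), about 0.2%.

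Shortened windows would be common on that assumption, and near-zero windows rare.

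**Event related only to a swab taken after the blood, section by section**
- *Non-serious, after b + 48:* not an AE (9.1); not a Reportable Event (9.3); not in Section 9's first paragraph, which needs a serious outcome; not in its second, which needs relatedness to the blood draw.
- *Non-serious, before b + 48:* an AE if relatedness in 9.1 is read as covering any study specimen, but still not in the second paragraph's IRB summary.
- *Serious, after b + 48 but within 48 hours of the swab:* an SAE with 24-hour Site PI evaluation under Section 9's first paragraph; a Reportable Event under 9.1 to 9.3. Either way Section 9 sends it to the IRB within 10 working days, or as local ethics rules require.

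**Narrow reading of 9.1.** If its closing words on relatedness refer back only to the blood collection, the arithmetic is irrelevant: no swab or urine event is ever an AE by virtue of that collection. The conflict with Section 9's first paragraph then becomes complete.

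**The case against.** The best defence is Section 10.8, which describes the blood draw as the study's sole intervention and treats everything else as standard care. On that view a blood-only clock is deliberate. It does not settle the matter. Section 4.3 makes the rapid tests a study requirement, 9.1 itself counts events after sputum induction, and the first paragraph of Section 9 refers to study specimens without restriction. Section 10.8 is one more passage to reconcile.

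Several limits on the point do stand, and they rule out stronger readings that a reader might infer:

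- *That late swabs generally have no AE window.* Zero is a boundary case. Postponement is an allowance, not the default, and a swab taken with or before the blood loses nothing.
- *That all 275 children are affected.* That is a ceiling; the documents give no collection times from which to estimate a number.
- *That Section 9 already covers a minor nosebleed after a swab.* It does not: the first paragraph is confined to serious outcomes and the second to the blood draw.
- *That a serious swab event loses its 24-hour evaluation.* The first paragraph of Section 9, on its own wording, grants it; Sections 9.1 and 9.2 together point the other way. This is a conflict, not a demonstrated loss.

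The Unanticipated Problem route in Section 9.4 is also open to some non-serious events, but only if they are unexpected, at least possibly related, and place subjects or others at greater risk than was known.

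**Conclusion.** The inconsistency is real and should be corrected. Under 9.1, a swab, urine or non-induced sputum specimen taken after the blood has b + 48 − s hours of AE coverage instead of 48. With blood at its 24-hour limit and the swab at its 48-hour limit, that is 24 hours; it reaches zero only at the extreme combination. The practical loss is mainly non-serious events, which can miss the AE definition and are left out of the IRB summary regardless of timing. Serious events still reach the IRB, but their classification differs between Section 9 and Sections 9.1 to 9.2.

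This assumes that relatedness in 9.1 extends to all study specimens, that enrolment blood is taken at one time (if at several, b is the last), and that a swab taken before the blood is not penalised. The Day 14 blood collection opens a new window but does not cover the enrolment swab. The matter is one of safety-event definition in a study that describes itself as minimal risk; no estimate, precision statement or algorithm result depends on it.

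**What to change.** In both 9.1 and the second paragraph of Section 9, replace the blood-only wording with *collection of any study specimen*. State that the 48 hours run from each specimen's own collection time and that relatedness is judged to that collection. This matches the first paragraph of Section 9 and covers blood, swab, urine and non-induced sputum. Changing 9.1 alone would not be enough, because non-serious swab and urine events would still be left out of the Continuing Review summary.

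Keep the separate sputum-induction sentence in 9.1, and say expressly that induced sputum stays under it, so that the general wording does not create a second clock for that procedure. Reconcile the statement in Section 10.8 about the sole study intervention with Section 4.3.

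The cost is a short edit in two places, a recorded collection time for each specimen, and a few more minor events to document.

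### Section 9.1 judges worsening after sputum induction against the pre-enrolment state, not the pre-induction state, and does not make clear how its 2-hour rule fits the 48-hour windows

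*Combined protocol and SAP*

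**What the plan says.** **Section 9.1** contains two rules. The first paragraph covers an event "within 48 hours of a study-related study blood specimen collection that is possibly, probably, or definitely related to the study specimen collection" and says that anything outside this 48-hour "window period will not be considered an AE for this study". The second paragraph opens with a contrast and deals with induced sputum. Its trigger is "worsening from the original condition prior to the enrollment is observed such as, but not limited to, increase in coughing or wheezing". The time limit that goes with this trigger reads: "it will be considered as AE for this study if occurred within 2 hours after sputum induction procedure". The paragraph closes by saying that for each such event "the RA needs to consult with the site PI or site Co-PI to determine AE or not".

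**Section 9** introduces SAEs through reportable events described as "events that occur within 48 hours of the study specimen collection and are possibly, probably, or definitely related to the study specimen collection", which the site PI evaluates within 24 hours of awareness. The next paragraph, on the Continuing Review summary, has instead "events that occur within 48 hours of the research blood draw and are possibly, probably, or definitely related to the research blood draw". Reportable Events and unanticipated problems "will be reported by the site PI to the IRB within 10 working days", or as local ethics rules require. The same limit is given for SAEs.

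**Sections 9.2 and 9.3.** An SAE must first be an AE related to specimen collection. A serious event that is not an AE is a Reportable Event.

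**Timing.** Section 4.6.2 and Table 1 require whole blood and serum within 24 hours of enrolment and let the other specimens, sputum among them, wait up to 48 hours.

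**Scope of the term.** Section 6.3 defines study specimens broadly enough to include sputum. Section 10.8 describes the blood draw as the sole study intervention.

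**The concern.** A reaction to a procedure is recognised by a change across that procedure. Section 9.1 measures a change from a state that may lie two days or more in the past, in hospitalised children whose pneumonia is being treated and can move either way. The rule can therefore err in both directions: it can pass over a reaction in a child who has improved, or count disease worsening that came before the induction.

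The second issue is the time limit. The 2-hour limit appears only in 9.1. Section 9 uses 48 hours and, on one reading, applies that to sputum too. Sites could then give the same serious deterioration different labels.

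At stake is uniform safety classification across hospitals for a study procedure in children aged 2 months to 5 years.

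**Working it through.** The plan gives no figure to reproduce. The check compares the definitions and adds up the stated time limits.

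**Inputs**
- b = hours from enrolment to the study blood draw, 0 to 24 (Section 4.6.2, Table 1).
- s = hours from enrolment to sputum induction, 0 to 48 (same places).
- g = s − b, the gap from blood to sputum.
- AE windows in 9.1: 48 h after blood; 2 h after induction.
- Window in Section 9, first paragraph: 48 h after specimen collection.

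**Age of the comparator.** At induction the pre-enrolment state is at least s hours old. At s = 48 it is 48 hours old or more.

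**Comparator, if the sputum sentence replaces the first paragraph of 9.1**
- A child improves after enrolment, then coughs or wheezes more within 2 hours of induction without passing the pre-enrolment state. This is not an AE. Unless serious, it is not a Reportable Event either.
- A child is already worse than before enrolment, from disease, when induction starts. This may be counted as an AE, because the sentence itself has no relatedness condition. The PI or Co-PI consultation is a filter, but it names no pre-induction reference.

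**Comparator, if the sputum sentence only adds to the first paragraph.** A related event is still caught up to hour b + 48, with no pre-enrolment comparator. This takes relatedness in that paragraph to cover an event caused by the induction. The blood window spans the full 2 hours after induction when s + 2 ≤ b + 48, that is, when g ≤ 46. With sputum at or after blood, the comparator decides the fate of a related event only if g > 46, which needs b < 2 and s > 46. If sputum comes first, it decides only for events before the draw.

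**Window, assuming that Section 9 includes sputum.** The Section 9 window ends at s + 48.

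| Reading of 9.1 | AE window ends at | Stretch that is an SAE in Section 9 but a Reportable Event under 9.1–9.3 |
|---|---|---|
| Replaces | s + 2 | (s + 48) − (s + 2) = 46 h, for any g |
| Adds, s ≥ b | max(s + 2, b + 48) | (s + 48) − max(s + 2, b + 48) = min(46, g) |

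In the second row, g = 0 gives 0 h, g = 12 gives 12 h, g = 24 gives 24 h, and g = 46 to 48 gives 46 h. If sputum comes first, counting only time after the draw, the uncovered stretch is max(0, b − s − 2), at most 24 − 0 − 2 = 22 h.

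**Window, if Section 9 means blood only.** This conflict disappears.

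**What differs by label.** As an SAE, the event has a stated site PI evaluation within 24 hours of awareness. As a Reportable Event, no such evaluation is stated. The IRB time limit is the same for both.

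**The case against.** The strongest reply is that little follows from this.

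- Serious events go to the IRB on the same timetable under either label, and a related, unexpected serious event may also be an unanticipated problem under 9.4. This stands.
- For non-serious events, the Continuing Review sentence names only the blood draw. Read literally, changing the sputum comparator alters no stated IRB report. This stands too; what remains is the AE record itself.
- Disease progression cannot become an SAE without a relatedness judgement, because Sections 9 and 9.2 both require one. This stands, so over-counting concerns non-serious AEs, and those pass through the PI or Co-PI consultation.
- Section 9 may mean blood only. The first paragraph of 9.1 starts from a blood specimen and then uses the general term, the second paragraph of Section 9 names the blood draw, and Section 10.8 points the same way. Section 6.3 points the other way. The text does not settle it.
- The additive reading catches most related events. This is correct if that reading applies. The contrast that opens the sputum sentence suggests a separate rule, but the protocol does not say so.
- The Manual of Procedures, which was not available, may already require a pre-induction assessment. It may, so the request for a CRF entry is conditional. The comparator written in 9.1 would still be the pre-enrolment one.

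**Conclusion.** The point holds, at minor severity. The comparator in 9.1 is the pre-enrolment condition, and nothing in the documents ties it to the child's state just before induction. Whether that changes a classification depends on whether the sputum sentence replaces or adds to the first paragraph. The window conflict depends on that and also on whether Section 9 includes sputum. Its size runs from 0 to 46 hours. These are permitted limits, not expected delays, and affected events cannot be counted because the documents do not say how many of the 275 children will have sputum induced.

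Three stronger conclusions are tempting and are not supported:
- A reader might infer that reactions in improving children are simply lost as AEs. That follows only on the separate-rule reading. Signs and vital signs are in any case collected daily in hospital, if available (Section 4.6.3).
- A reader might infer a firm 46-hour contradiction. It needs Section 9 to include sputum and either the separate-rule reading or a blood-to-sputum gap of at least 46 hours.
- A reader might infer that serious events escape the IRB. They do not: both routes carry the limit of 10 working days or the local requirement.

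No algorithm or etiology analysis is affected.

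**What to change.** 1. In 9.1, make the reference for worsening the child's status immediately before the sputum induction. Record it on the CRF if the CRF, worksheet or Manual of Procedures does not already capture it.
2. State whether the induced-sputum sentence adds to or replaces the first paragraph of 9.1.
3. State whether specimen collection in the first paragraph of Section 9 includes sputum.
4. Reconcile Sections 9, 9.1 and 9.2 to one stated window for induced sputum. No view is taken here on which window is right.

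The cost is a few words of protocol text and at most one CRF line. The number of recorded AEs could move either way: reactions in improved children would be added, and disease worsening before induction would drop out.
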